A special consideration during cardiac surgery is that organ blood flow is also often affected by non-pulsatile flow or hypotension. Lele et al., in a controlled hypotension model in dogs, found that EA helped maintain better blood flow to the stomach and kidney, resulting in reduced apoptosis in those organs. Further, the apoptosis that was observed in the control animals' brains did not occur in the animals receiving EA. Points used were large intestine (LI)-4, ST-36 spleen (SP)- 6 and LI-11 stimulated bilaterally at 2 Hz with 3-5 mA.¹⁴

Research Plan:

This study will help to identify whether electroacustimulation is a beneficial anesthesia adjunct in children undergoing procedures on their congenital heart defects.

Electroacustimulation is a technique with minimal risks, which enhances the body's innate abilities to deal with the stresses and pain of surgery. Our goal is to optimize care for those patients with congenital heart disease by increasing *comfort* and *reducing complications*. This study will examine comfort using age appropriate pain scoring systems. The complications this study will focus on are myocardial injury which will be assessed by measuring Troponin levels, and renal injury assessed using AKIN criteria

Treatment Groups:

Subjects will be randomized. Randomization will be done using block randomization with block sizes between 4 and 8. The sham procedure will use the identical set up as the treatment group, but those participants in the sham group will not receive the electro-stimulation.

Group 1: Will have electrodes placed at Pericardial 4 and 6, Large Intestine 4, and Stomach 36 and receive electroacustimulation (treatment) frequency will be at 2Hz and 100 Hz the amplitude will be 1000mA.

Group 2: Will have electrodes placed at Pericardial 4 and 6, Large Intestine 4, and Stomach 36 and receive sham electroacustimulation (control) will not have stimulation.

Duration of Treatment:

The duration of treatment (stimulation or sham) for subjects will be length of surgical procedures on their congenital heart defects. Patients will be followed for 6 hours to collect data on myocardial injury and 48 hours to collect data on pain, and renal injury.

Objectives:

Primary Objective:

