The primary objective of this study is to identify whether electroacustimulation is a beneficial anesthesia adjunct in children undergoing procedures on their congenital heart defects. Does it decrease myocardial injury and or need for myocardial support. Differences between the groups Troponin I levels pre-operative and six hours postoperative will be evaluated.

Secondary Objectives:

1) Evaluate the incidence discomfort in the post- operative period.

To evaluate the incidence and severity of pain assessed by using age appropriate West Virginia University Hospital approved nurse guided pain scoring the Neonatal/Infant Pain Scale (NIPS) (children age birth to 2 months) FLACC (2 months to 7 years or unable to communicate, or VAS(age 8-18) every 2 hours for 48 hours post procedure.

2) Determine the incidence of Acute kidney injury (AKI) between these two treatment groups. Acute Kidney Injury will be evaluated by AKIN criteria. Creatinine and urines will be measured at 6, 12, 24 and 48 hours after bypass.

Need for post-operative myocardial support:

To assess the need for myocardial support an inotropic score will be used and compared between the two groups. The Inotropic score will be evaluated every 6 hours for 48 hour between the 2 groups

Study Design:

This is a single site, randomized, blinded, sham controlled, parallel group study to identify whether electroacustimulation is a beneficial anesthesia adjunct in children undergoing procedures on their congenital heart defects.

Study subjects age's birth to eighteen years, undergoing cardiac surgery for their congenital heart lesions will be considered for entrance into the study. The randomized subjects will receive either electrostimulation or sham during their surgery for CHD. Subjects are expected to remain in the hospital 48 hours post procedure. Standard of care blood samples will be obtained pre-operative and post-operative. The only study specific blood sample will be Troponin I levels which will be obtained presurgically after the lines have been placed and a 6 hours post bypass/aortic clamp removal. Urine samples will be obtained pre-surgically after placement of the Foley and every 6 hours post bypass for 48 hours while the Foley catheter is still in place .

Number of Subjects planned:

Approximately 108 patients, over the two years, with randomization of 54 allocated to each group.

- Electroacustimulation (treatment) frequency will be at 2Hz and 100 Hz the amplitude will be 1000mA.

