- Sham electroacustimulation (control) will not have stimulation

Study Population:

Inclusion criteria:

Subjects must fulfill all of the following inclusion criteria to be eligible for participation in the study:

- 1) Patients 0-18 years of age undergoing procedures on their congenital heart defects.
Additionally, patients with coarctation of the aorta for repair will be considered as a separate group and eligible for enrollment.
- 2) Willing to provide written Assent/Consent in English.

Exclusion criteria:

Subjects will be excluded if they fulfill any of the following exclusion criteria:

- 1) Patients with skin lesion over more than 50% of acupuncture sites.
- 2) Patients in renal failure.
- 3) Patients on chronic opioid therapy.
- 4) Unwilling to provide written Assent/Consent in English.

Concomitant Treatment:

All subjects will receive a standard anesthetic of propofol, remifentanyl and dexmedetomidine at doses needed to maintain a stable BIS number and lack of movement. When possible neuromuscular blocking agents will not be used. A morphine infusion will be used for postoperative pain control based on need. Those allergic to morphine will receive a substitute opiate by continuous infusion.

Study Procedures:

Screening:

Review of consent form- Subjects that provide written assent/consent and meet all inclusion and no exclusion criteria will be included into the study. Subjects may withdraw consent to participate at any time. Participation in the study is voluntary. Adverse events will be recorded after informed assent/consent obtained.

Surgery: Treatment/Sham

Eligible subjects will undergo blood sampling (3.5cc) and urine sample (0.5-2cc) will be obtained prior to stimulation/sham.

All subjects will have electroacustimulation pads applied at four points bilaterally: pericardial 4 (PC 4), pericardial 6 (PC 6), large intestine 4 (LI 4) and stomach 36 (ST 36). No needles will be used. ([Appendix A; 1](#))

Subjects will be randomized. Randomization will be done using block randomization with block sizes between 4 and 8. The sham procedure will use the identical set up as the treatment group, but those participants in the sham group will not receive the electro-stimulation. Stimulation/sham will begin as soon as possible after induction of anesthesia and obtaining baseline laboratory samples of urine and blood.

Group 1: Receive electroacustimulation (treatment) frequency will be at 2Hz and 100 Hz the amplitude will be 1000mA.

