Group 2: Receive sham electroacustimulation (control) will not have stimulation. Subjects will undergo procedures on their congenital heart defects.

Blind:

The anesthesia provider will be blinded as to whether the electroacustimulation device is actually turned on or not. The research coordinator will hold the blind. The electroacustimulation machine will be placed in an opaque bag to secure the blind. The current is below the threshold to stimulate the muscle so that no movement will be visible. It is also below the sensory threshold so that it will not produce any discomfort in the subjects.

Stimulation/Sham will be continued until the patient is ready for transport to the PICU.

Post-Operative: PICU

Stimulation/Sham will be discontinued.

PICU care givers will be blinded as to which group the patients were randomized.

Subject comfort will be assessed using age appropriate West Virginia University Hospital approved nurse guide pain scoring based on Universal Pain Assessment Tool or the Neonatal/Infant Pain Scale (NIPS) will be recorded in the electronic medical record (EMR) every 6 hours for 48 hours.

The amount of opiate infused, Nausea, Vomiting, and urine output will be assessed every 6 hours for the first 48 hours and recorded in the EMR.

Research blood samples for troponin I will be obtained at 6 hours post surgery. Total amount of 7cc of blood will be

obtained for this study. WVUH lab will process samples.

Research urine samples (.05-2cc) will be collected at 6, 12, 24, and 48 hours after bypass. The urine samples will be stored in a -80 degree freezer and analyzed by ELISA testing at the end of the study for Superoxide dismutase, Neutrophil gelatinase – associated lipocalin (NGAL), WNT4.

AKIN criteria will be used to evaluate AKI every 6 hours. Inotropic score will be recorded every 6 hours.

Daily chest x-ray will be used to assess pulmonary status.

The AKIN criteria, inotropic scores, chest x-ray and creatinine levels, (used for AKIN), are standard of care measurements and the data will be collected for this research project.

An Electrostimulation Documentation Guide has been developed for the staffing. (Appendix A2)

Tool/Instruments to be used in data collection:

Tools and instruments for data collection: secured Excel data base; Neonatal/Infant Pain Scale (NIPS); AKIN stage; Inotropic Scores; RACHS categories (Appendix A3-6).

Variables:

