To address the overall difference between the control and the acupuncture group, we will look at the score changes between baseline and 48 hours. For the continuous outcomes, a t-test based on the difference in outcome will be used to compare the two treatment groups. For the categorical outcomes, a logistic regression model (generalized linear model with binary or multinomial outcome) will be used to compare the two treatment groups' at baseline and 48 hours. The generalized linear hypothesis methodology will be used to contrast the two time points. This approach will provide consistency of modeling methodology for the secondary analyses. Adjusted models will be considered (e.g. glm regression with identity and/or logit links) to account for any data imbalances, potential confounders, etc. Minimally, a RACHS score adjustment will be assessed for its relevance.

A secondary analysis will be used to describe the longitudinal (repeated measures) outcome trends. A generalized linear mixed-effects regression model will be used for longitudinal data. Both unadjusted and adjusted trends will be assessed. We will account for both heteroscedasticity and autocorrelation variance-covariance structures. The generalized linear model approach will permit trend characterizations for either continuous or categorical outcomes under the same generalized linear model framework.

[figure not shown]
All results, predicated on formal hypothesis testing methodology, will use an alpha-level of 0.05 for statistical significance. Bonferroni or Scheffe adjustments will be used, when appropriate, to retain the family-wise alpha level of 0.05 when performing multiple tests under the same global hypothesis or construct. Every effort will be used to ensure all relevant information is collected. In the event of missing data, generalized estimating equations for longitudinal analysis will be used. All statistical analysis will be done using the most recent version of the R language for statistical computing and graphics.

Tentative time table: Approximately 2 years to enroll 108 subjects.

[figure not shown]
References:

- 1) Instruction manual for KWD-808I Multipurpose health device, Ying Di page 21.
http://www.ib3health.com/products/Acupunctoscope/KWD808_I.asp#808I_Instruct [Accessed Sept. 5, 2016]

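### The SAP's one main comparison, change from baseline to 48 h, does not match the schedule or the stated objective for troponin I, opioid dose, AKI, pain and inotropic score

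*Combined protocol and SAP*

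**What the plan says.** The Statistical analysis plan section answers the question of overall difference between arms in one way: "we will look at the score changes between baseline and 48 hours". Continuous outcomes get a t-test on the difference. Categorical outcomes get a logistic or multinomial model at the two time points, with a contrast between them. A mixed model for repeated measures follows, labelled secondary and meant to describe trends.

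The Primary Objective asks "Does it decrease myocardial injury and or need for myocardial support" and then gives its contrast: "Differences between the groups Troponin I levels pre-operative and six hours postoperative will be evaluated". Duration of Treatment agrees: "Patients will be followed for 6 hours to collect data on myocardial injury and 48 hours to collect data on pain, and renal injury".

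The 6 h draw is timed in two ways. Study Design has "Troponin I levels which will be obtained presurgically after the lines have been placed and a 6 hours post bypass/aortic clamp removal". Post-Operative: PICU has "Research blood samples for troponin I will be obtained at 6 hours post surgery".

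The second secondary objective is the incidence of AKI. The Sample size section uses a morphine-equivalent dose in mg/kg.

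**The concern.** A baseline-to-48 h change needs a value at both ends, and the change (or the 48 h value) must be the quantity the objective asks about. For several outcomes one of these fails, and they include the troponin measure of the primary objective and the opioid dose that sets the sample size.

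An analyst who follows the main rule literally gets no troponin test, an opioid test on a small final slice of the dosing record, and an AKI result that is not incidence. An analyst who departs from it must choose the troponin time anchor and the opioid summary. The text of the main rule settles neither, and such choices could be made after allocation is known.

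**Working it through.** **1. The plan's own figure.** Inputs from Sample size: means 0.71 and 0.57 mg/kg, SDs 0.3 and 0.2, two-sided alpha 0.05, power 80%, unequal-variance t-test.

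- Difference: 0.71 − 0.57 = 0.14 mg/kg.
- Normal approximation: n = (1.960 + 0.842)² × (0.3² + 0.2²) / 0.14² = 7.85 × 0.13 / 0.0196 ≈ 52.1, so 53 per arm.
- Welch test, noncentral t, 53 per arm: SE = √(0.13/53) = 0.0495; noncentrality 0.14/0.0495 = 2.83; Satterthwaite df = 0.13² × 52 / (0.09² + 0.04²) = 90.6; power 79.9%.
- The same at 54 per arm: SE = 0.0491; noncentrality 2.85; df = 92.3; power 80.6%.

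So 54 per arm (108 in total) is the smallest size that reaches 80%. It is the size for a direct between-arm comparison of dose level, with no baseline term.

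**2. Schedule against the rule.** Baseline means before stimulation or sham. The documentation guide's baseline list holds only creatinine, urine sample, RACHS score and cyanosis.

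| Outcome | Baseline scheduled | 48 h scheduled | What the rule yields |
|---|---|---|---|
| Creatinine, NGAL, WNT4, superoxide dismutase (Appendix B) | yes | yes | a defined change |
| Troponin I | yes | no | no change can be formed |
| Opioid use | no | last interval only | no change unless a baseline is assumed |
| AKIN stage | no | yes | stage at 48 h, not incidence |
| Pain | no | yes | no observed change |
| Inotropic Group 1-5 | no | yes, from the highest support in each 24 h period | between-arm comparison only |

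**3. Troponin draws.** The blood volumes agree with two draws. Surgery: Treatment/Sham has "Eligible subjects will undergo blood sampling (3.5cc) and urine sample (0.5-2cc) will be obtained prior to stimulation/sham", and the PICU section gives the study total: "Total amount of 7cc of blood will be" obtained. 7 / 3.5 = 2. Scheduled 48 h values: 0 of 108 patients. Troponin is also absent from the outcome list under Variables, from the documentation guide and from Appendix B.

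**4. Opioid.** Appendix B records use 2-hourly as a rate; the PICU section records the amount 6-hourly. The final entry therefore covers 2/48 = 4.2% or 6/48 = 12.5% of the window. The Sample size section does not say what period its dose covers.

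**5. AKI.** Six-hourly staging over 48 h gives 48/6 = 8 readings, and the rule uses one. The Background puts AKI of at least stage 1 at 50% after cardiovascular surgery. On that figure an arm of 54 would have 27 cases. If a share f resolves before 48 h, the 48 h reading counts 27 × (1 − f). The documents give no value for f, so the shortfall cannot be sized, but it is zero only if f is zero.

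**The case against.** The strongest reply has five parts.

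- **Troponin.** This is one combined document. The Primary Objective states the pre-operative to 6 h contrast, and the SAP's t-test on a difference could be applied to it. That stands as far as intent goes. The SAP's stated window still contradicts it, and the two time anchors remain.
- **Mixed model.** It is pre-specified and can use the repeated pain, opioid, inotropic and AKIN data without a baseline. That stands, and it softens the conflict. It is labelled secondary, however, and it supplies neither a 48 h troponin value nor AKI incidence.
- **Inotropic score.** A reader might infer that this analysis cannot be run at all. The documents do not support that. Appendix B makes it a five-level group, and the SAP's categorical method compares arms at each time point, so only the baseline limb lacks data. A reader might also take the score to be a settled primary measure. The Primary Objective mentions myocardial support but names only troponin I; the score is described after the secondary objectives, so its status is unclear.
- **Opioid.** Chronic opioid therapy is an exclusion, so baseline could be taken as zero. That is an assumption, since acute pre-operative use is not excluded. Under it the change equals the 48 h entry, which is still only the final interval.
- **Tally.** Counting all listed outcomes that fail the rule would exaggerate. Pneumonia, time to extubation and PICU stay are an event and two durations that nobody would difference.

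**Conclusion.** The point holds and should be settled before analysis. Followed as written, the main comparison gives no troponin test, gives an opioid test on at most 12.5% of the window even with an assumed zero baseline, and gives an AKI quantity other than the stated incidence. For pain and inotropic score the baseline part has no data, though both can be compared between arms after surgery.

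Three limits apply. A reader might infer that the sample size is wrong; it is not on its own inputs, and the mismatch lies between it and the SAP's main test. The AKI conclusion assumes that each 6-hourly stage describes the patient at that time; if the 48 h stage was meant to carry the worst stage forward, the plan should say so. Fit is also not certain for the urine biomarkers, because Study Design ties urine collection to the Foley catheter remaining in place, so some 48 h values may be missing. A figure in the SAP section was not available for this reading; the conclusion rests on the text.

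**What to change.** Keep the baseline-to-48 h rule for creatinine, NGAL, WNT4 and superoxide dismutase. For the rest, state in the SAP:

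- **Troponin I:** compare arms on the 6 h value adjusted for the pre-operative value, or on the pre-operative to 6 h change. Reconcile the two time anchors into one. Add troponin to the outcome list, the documentation guide and Appendix B.
- **Opioid:** compare cumulative mg/kg over 0-48 h between arms, after confirming the period that the sample-size dose covers.
- **AKI:** compare any (or worst) AKIN stage over 0-48 h between arms.
- **Inotropic support:** compare Group 1-5 between arms with no baseline term, after stating whether IS or VIS is used.
- **Pain:** use a post-operative between-arm comparison with no baseline change, for example the existing mixed model, after reconciling the 2-hourly schedule (Secondary Objectives, Appendix B) with the 6-hourly one (PICU section, documentation guide).

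The cost is text edits to the protocol, documentation guide, Appendix B and SAP. All of it uses data already scheduled, so no samples or visits are added.

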Predicated on the primary aim, the sample size for this pilot study we used a two-sided two-sample t-test with unequal variance t-test with an alpha level of 0.05 and power of 80%. A morphine equivalent dose of 0.71 mg/kg was used for the control group and 0.57 mg/kg for the acupuncture group. This represents a conservative 20% change between the control and acupuncture group. The standard deviation of the control group was estimated to be 0.3 mg/kg for the control group and 0.2 for the experimental group. **The total estimated sample size is 108 patients, over the two years, with 54 allocated to each group.** Historically, we would have had a potential enrollment and retention of approximately 74 patients per year accounting for a 25% non-consent rate and a 2% drop-out rate. This project is well powered for statistical significance and feasibility for a 2-year study.

Data collection:

The data will be retrieved from the EMR and imported or entered into a secured EXCEL database.

Statistical analysis plan:

For all aims, univariate statistics (e.g. mean, median, standard deviation, min, max and skew) will be used to describe the collected data. Parametric approaches (e.g. t-test, Pearson's correlation, and chi-squared test) will be used when the data satisfy the required statistical assumptions; they will be used to compare the demographic and clinical characteristics between treatment and control. If the distributional assumptions are untenable, then the Mann-Whitney test, Spearman

correlation, and Fisher's exact test will be used. We will use the Box-Cox or the exponential transformation when the absolute value of skew is greater than 0.4.

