Appendix B: Variable descriptions.

Variable	Description	Measurement times	Measurement scale
Outcomes			
Pain score	Age appropriate WVUH approved Nurse guided pain scoring. The pain scale score will be recorded in the electronic medical record.	Every 2 hours for 48 hours	Tool: NIPS score, FLACC score or Visual analog scale Scale: 0-10; 0=none, 10=worst pain
Inotropic score	IS or VIS 1 st 24 hours IS or VIS 24-48 hours	Every 6 hours for the first 48 hours of observation	Group 1-5
Narcotic use	Opiate use will be its own variable as well as a surrogate for pain as comfort will be maintained at a score less than 40% of the max possible score for the pain scoring system used.	Every 2 hours for 48 hours	mcg/kg/hr
Creatinine/Urine	Assessment of AKI-renal complication	Baseline, 6, 12, 24, and 48 hrs post CPB	Creatinine mg/dl Urine ml/kg/hr
Neutrophil gelatinase-associated lipocalin (NGAL)	Renal biomarker-urine sample collected and frozen-renal complication	Baseline, 6, 12, 24, and 48 hrs post CPB	ELIZA
WNT4	Renal Biomarker-urine sample collected and frozen-renal complication	Baseline, 6, 12, 24, and 48 hrs post CPB	ELIZA
AKIN score	Acute kidney injury (AKI)-renal complication	Every 6 hours for the first 48 hours of observation (EMR)	Stage 1-3
Superoxide dismutase	Renal Biomarker-urine sample collected and frozen-cardiac injury-complication	Baseline, 6, 12, 24, and 48 hrs post CPB	ELIZA
Pneumonia	complication	Daily (Chest x-ray)	Indicator: 0=No, 1=Yes
Intubation time	The date and time of intubation as part of surgery prep.	Obtained from patient's EMR	Date and time
Extubation time	The date and time of extubation as part of surgery prep.	Obtained from patient's EMR	Date and time
PICU arrival	The date and time of arrival in the PICU	Obtained from patient's EMR	Date and time
PICU discharge	The date and time of discharge from the PICU	Obtained from patient's EMR	Date and time
Other variables			
Age	Age of the patient	Baseline	In days
Sex	Sex of the patient	Baseline	Indicator: 0=Male, 1=Female
Cardiac defect	Type of CD	Baseline	Diagnosis

Cyanosis	Blueness of skin- based on room air oxygen level less than 90% sat-guide for opiate amount-complication	Baseline	1=yes 2=no
RACHS score	Randomization Guide	Baseline	Categorical: 1 through 6
CPB start time/ Aortic clamp time	Cardiopulmonary bypass (CPB) start time/ Placement of aortic clamp	Obtained from patient's EMR	Date and time

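### For creatinine, NGAL, WNT4 and superoxide dismutase the main test is a raw baseline-to-48 h change; a baseline-adjusted contrast over 6 to 48 h from the mixed model already planned would use the data better

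*Combined protocol and SAP*

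**What the plan says.** The Statistical analysis plan sets one rule for the overall difference between arms: "we will look at the score changes between baseline and 48 hours". For continuous outcomes the test is a t-test on that difference. The rule names no outcomes, so it covers every continuous one. The Variables section lists creatinine, NGAL, WNT4 and superoxide dismutase among the outcomes.

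Appendix B gives the measurement times for all four as "Baseline, 6, 12, 24, and 48 hrs post CPB". The values between baseline and 48 h are taken up only in the next paragraph of the plan: "A secondary analysis will be used to describe the longitudinal (repeated measures) outcome trends". That analysis is a generalized linear mixed-effects model, unadjusted and adjusted, allowing for heteroscedasticity and autocorrelation. The plan does not say which treatment contrast, time point or summary will be read from it.

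Formal tests are at 0.05, with Bonferroni or Scheffe adjustment where appropriate. The Sample size section rests on opioid dose and gives no power for any renal marker.

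**The concern.** Three of the four post-bypass values of each marker play no part in the main comparison, and the value that does is the one furthest in time from bypass and from stimulation, which ends before transfer to the PICU. Subtracting the raw baseline also adds noise that a regression on baseline would remove.

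If an effect is present in the first day and has shrunk by 48 h, the main test will probably be negative. The secondary model might show the effect. With no contrast named in advance, though, a positive result there would be chosen after the fact and would compete with a negative main result.

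There is also a practical risk. Study Design limits urine collection to the time the Foley catheter is in place, so the 48 h urine may be the sample most often missing. A child without it has no change score for the three urine markers. This is an inference; the documents give no rate.

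**Working it through.** **The plan's own figure.** Inputs from the Sample size section: "A morphine equivalent dose of 0.71 mg/kg was used for the control group and 0.57 mg/kg for the acupuncture group", and SDs of "0.3 mg/kg for the control group and 0.2 for the experimental group". The difference is 0.71 − 0.57 = 0.14. At 54 per arm the standard error is √((0.3² + 0.2²)/54) = 0.0491, so the noncentrality is 0.14/0.0491 = 2.85. The unequal-variance t-test then has 80.6% power; at 53 per arm it has 79.9%. The stated 54 per arm, 108 in total, is reproduced. It concerns opioid dose, not these markers.

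**Assumptions for the markers.** The documents give no SDs, effects or correlations for them. I take SD 1 at every time, on the analysis scale, and a common correlation r of 0.3, 0.5 or 0.7 between any two times, baseline included. There are 54 per arm, complete data, and a two-sided test at 0.05.

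**Variance per child of each summary**

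- Raw change to 48 h: 2(1 − r)
- 48 h value adjusted for baseline: 1 − r²
- Mean of 6, 12, 24 and 48 h adjusted for baseline: (1 + 3r)/4 − r²

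| r | Raw change | Adjusted 48 h | Adjusted mean of four |
|---|---|---|---|
| 0.3 | 1.40 | 0.91 | 0.385 |
| 0.5 | 1.00 | 0.75 | 0.375 |
| 0.7 | 0.60 | 0.51 | 0.285 |

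The first two differ by 2(1 − r) − (1 − r²) = (1 − r)², which is never negative. So at 48 h the raw change cannot beat baseline adjustment, whatever r is.

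**Power.** With V the variance above, d = effect/√V, and the noncentrality is d × √(54/2) = 5.196d. There are 106 degrees of freedom, or 105 with the covariate. Worked case, constant 0.5 SD effect, r = 0.5:

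- Raw change: d = 0.5/√1.00 = 0.50, noncentrality 2.60, power 73%.
- Adjusted mean: d = 0.5/√0.375 = 0.816, noncentrality 4.24, power 99%.

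For the other profiles the adjusted mean sees the average effect:

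- Fading: (0.5 + 0.4 + 0.25 + 0.1)/4 = 0.3125
- 48 h only: 0.5/4 = 0.125

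| Effect in SD at 6, 12, 24, 48 h | Raw change (planned) | Adjusted 48 h | Adjusted mean of four |
|---|---|---|---|
| 0.5, 0.5, 0.5, 0.5 | 59 / 73 / 91% | 77 / 84 / 95% | 99 / 99 / >99% |
| 0.5, 0.4, 0.25, 0.1 | 7 / 8 / 10% | 8 / 9 / 11% | 74 / 75 / 85% |
| 0, 0, 0, 0.5 | 59 / 73 / 91% | 77 / 84 / 95% | 18 / 18 / 23% |

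Entries are for r = 0.3 / 0.5 / 0.7.

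**Sensitivity to the correlation pattern.** If correlation decays with time at 0.8 or 0.9 per 12 h, a normal approximation for the constant effect gives 67% or 88% for the raw change and over 99% for the adjusted mean. The direction is the same.

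**Sensitivity to multiplicity.** With Bonferroni over four markers the level is 0.05/4 = 0.0125. By the same formula, the constant effect has 37 / 52 / 79% power in the raw change and 95 / 95 / 99% in the adjusted mean. For the fading effect the figures are 2 / 2 / 3% and 53 / 55 / 69%.

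**The case against.** The strongest objection is that the gain depends on the shape of the effect, and the documents do not establish that shape for any renal marker. The Background's evidence of fading is left ventricular performance in dogs, lost over 120 minutes after stimulation stopped. Taken literally, that would remove an effect by 6 h as well. The Background also cites a valve-surgery trial with lower inotropic scores at 48 h after stimulation given before surgery. The protocol itself sets 48 hours as the follow-up for renal injury. If the effect is late, the average is the weaker test, and an equal-weight mean puts three quarters of its weight on the first day. This stands, and it is why the adjusted 48 h difference must stay in the report.

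A reader might also infer more than the documents support:

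- **That an early effect would be missed altogether.** The planned mixed model uses all time points and formal tests are allowed at 0.05, so it could find one. What is missing is a named contrast.
- **That renal protection is decided on one sample.** The stated renal objective is the incidence of AKI by AKIN criteria, a separate outcome with its own categorical analysis. NGAL, WNT4 and superoxide dismutase appear in no objective, and Appendix B ties superoxide dismutase to cardiac injury as well.
- **That stored samples are wasted on all four markers.** Creatinine is a standard-of-care measurement; only the urine is frozen and assayed. The urine values at 6, 12 and 24 h are still analysed, in the secondary model.
- **That the change score is always the noisiest choice.** Above r = 0.5 its variance, 2(1 − r), is below that of a single unadjusted value. It loses to baseline adjustment, not to every alternative.

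**Conclusion.** The point holds for the choice of main comparison for these four markers. Replacing the raw change by baseline adjustment at 48 h is a gain whatever the effect profile: from 59, 73 and 91% to 77, 84 and 95% for 0.5 SD at 48 h. Averaging over the four times adds power if the effect is constant, and adds much more if it fades. It costs power if the effect appears only at 48 h (18 to 23% against 59 to 91%). The sizes rest on assumed SDs, correlations and effect profiles; the ordering of raw change against baseline adjustment does not.

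The 108-patient sample size is untouched, because it was derived for opioid dose and reproduces. Nothing here shows that a renal effect will have gone by 48 h. The point is worth acting on because the change is cheap, but it concerns secondary outcomes in a trial that the Sample size section calls a pilot.

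**What to change.** For creatinine, NGAL, WNT4 and superoxide dismutase, state in the Statistical analysis plan:

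1. The main comparison is the treatment difference averaged over 6, 12, 24 and 48 h. It comes from the mixed model already planned, with the baseline value as covariate, time as a factor and a treatment-by-time term.
2. The scale for each marker follows the plan's existing skew-based transformation rule and is the same at all times.
3. The four time-specific differences, including the baseline-adjusted 48 h difference, are reported as supportive. This covers a late effect that the average would dilute.
4. The plan's Bonferroni adjustment is applied across the four markers.

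The cost is wording only. Patients, samples, assays and model are unchanged. The price in inference is the lower power of the average for an effect confined to 48 h, which the plan should acknowledge.
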